5.1 Inclusion Criteria

Participants are eligible to be included in the study only if all the following criteria apply during the 48-hour study Screening Period:

Informed Consent

- Participant (or legally authorized representative) provides signed informed consent prior to the initiation of any study assessments for participation in the study.

Age

- Are ≥ 18 to ≤ 75 years of age, at the time of signing the informed consent.

Type of Participant and Disease Characteristics

- Has laboratory-confirmed SARS-CoV-2 infection as determined by nucleic acid amplification test, polymerase chain reaction, antigen test, or other commercial or public health assay (based on locally accepted guidelines) in a sample collected < 10 days prior to randomization.
- Documentation of chest imaging consistent with COVID-19 pneumonia (as per locally accepted guidelines). If chest imaging is not available during Screening, please discuss with

Medical Monitor or designee regarding evidence of probable COVID-19 pneumonia for study participant eligibility.

5. Not on mechanical ventilation (invasive or noninvasive), or ventilation, or ECMO, nor (based on medical judgement of admitting physician) anticipated to be in the next 24 hours.
6. An SpO₂ < 94% in room air AND able to maintain a PaO₂/FiO₂ ≥ 150 (or equivalent SpO₂/FiO₂ ≥ 190) with a maximum FiO₂ 0.4. These readings may be obtained after exertion by the participant. Note: if participant is on chronic low O₂ therapy (≤ 2 L), assess their current baseline O₂ requirements for eligibility.
7. Requiring hospitalization (i.e., in the process of hospital admission or already admitted).

Birth Control based on Sex at Birth

8. a. Female Participants:

- Not a woman of childbearing potential (See [Appendix 2](#)).

OR

- If a woman of childbearing potential:

- Is using a depot contraceptive or extended cycle oral contraceptive from before the first dose of the study intervention(s).
- Agree not to become pregnant or donate eggs (ova, oocytes) for reproduction for a full 60 days.
- Use a highly effective contraceptive method (i.e., with a failure rate of < 1% per year) as described in [Appendix 2](#) for the duration of the study (a full 60 days), either with:
 - A daily use hormonal contraception from before the first dose of the study intervention(s),

OR

- Uses a barrier method during the length of the study (a full 60 days).

b. Male Participants:

- Agree to refrain from donating sperm for at least 90 days.

PLUS, either

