Appendix 5 Protocol Amendments History

The information for the current amendment is on the title page.

Changes from Version 2.0 to Version 3.0 Included in the Amendment

Section # and Name	Description of Change	Brief Rationale
Section 1.1 Synopsis	Included that participants on RECOVERY Trial dexamethasone dosing equivalent of corticosteroids may be eligible for enrollment.	Clarification of eligibility for enrollment.
Section 1.1 Synopsis	Increased the duration of the study to 15 months.	Due to protracted enrollment times.
Section 1.2 Schedule of Assessments	Included Hospital Discharge (HD) and HD assessment details. Amended details for requirement for chest imaging documentation. Updated ECG schedule. Updated cross reference.	To gather critical biomarker data and to align with various local standard of care guidance regarding chest imaging. To align ECG schedule with PK sampling.
Section 2.2.2 Potential Therapeutics	Amended details of antivirals and immunomodulating drugs.	Updated to describe recent clinical study results.
Section 3.2 Part B Objectives	Included PK parameters on Day 3 for Part B.	To reflect sampling on Day 3 if discharge is anticipated before Day 7.
Section 4.1 Overall Design Section 9.1.3.3 Pharmacokinetics	Included pre and postdose PK samples on Day 3.	To guarantee collection of Part B PK data if participant is discharged before Day 7.
Section 4.1 Overall Design Section 4.4 Early Hospital Discharge Assessments Section 5.5.4 Hospital Discharge	Clarified that participants discharged prior to Day 14 should have HD assessments performed.	To gather critical biomarker data.
Section 4.4 Early Hospital Discharge Assessments	New section added.	To clarify assessments performed at early discharge.
Section 5 Study Population Section 5.1 Study Population Section 5.5.1 Recruitment	Increased upper age limit for study participants to ≤ 75 years.	Based on study to date, study intervention is well tolerated; therefore, the age restriction is expanded up to 75 years of age, to reflect a higher risk group for COVID-19 pneumonia.
Section 5 Study Population	Included a guidance chart for FiO ₂ with regard to O ₂ delivery.	To facilitate enrollment.
Section 5.1 Inclusion Criteria	Expanded range of tests for SARS-CoV-2 infection.	To align with the range of tests that have become available.

Section # and Name	Description of Change	Brief Rationale
Section 5.1 Inclusion Criteria	Clarified inclusion criteria with regard to O ₂ therapy.	To facilitate enrollment.

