6.3 Final Analysis

This analysis will be the main analysis. All planned analyses identified in the study protocol and in this IAP will be performed only after the last participant has completed the safety follow up period with all study data in-house, and the database will be locked for the analysis.

A data review meeting will be held prior to any database lock.

7 Changes to the Planned Analyses in the Clinical Study Protocol

The inclusion of all stratification factors is identified as a potential source of problems in the implementation and interpretation of statistical models used to analyze efficacy. For this, use of corticosteroids before randomization and country will only be included, as deemed the most relevant factors, while presence of obstructive lung disease and use of antiviral therapy before randomization will be analyzed as subgroups.

8 Analysis Populations and Subgroups

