8.2 Subgroup Definition and Parameterization

The following factors, based on data collected on the eCRF, will be used as cofactors for all the stratified analyses:

- Treatment with corticosteroids therapy within 48 hours from randomization (as collected in the ‘Randomization’ eCRF page)
 - Corticosteroids dose \leq 15 mg of prednisone-equivalent (reference level)
 - Corticosteroids dose $>$ 15 mg of prednisone-equivalent

- Country
 - United States of America (reference level)
 - Philippines
 - Brazil

The following subgroups then, including the two stratification factors defined above and based on information collected at baseline, will be defined:

Comorbidities:

- Presence of obstructive lung disease (as collected in the ‘Medical History’ eCRF page)
 - No (reference level)
 - Yes

- Obesity based on BMI
 - No: Body Mass Index (BMI - derivation described at Section 11.1) $<$ 30 kg/m² (reference level)
 - Yes: BMI \geq 30 kg/m²

- Diabetes co-morbidity at study entry (as collected in the ‘Medical History’ eCRF page)
 - No (reference level)
 - Yes

- Heart diseases co-morbidity at study entry (as collected in the ‘Medical History’ eCRF page)
 - No (reference level)
 - Yes

- Hypertension co-morbidity at study entry (as collected in the ‘Medical History’ eCRF page)
 - No (reference level)
 - Yes

- Number of relevant comorbidities (derived for each participant counting the number of comorbidities among the ones listed above, including obesity based on BMI):
 - No (reference level)
 - Yes: 1 or 2
 - Yes: more than 2

Use of Relevant Therapies at baseline:

- Treatment with corticosteroids therapy within 48 hours from randomization (as collected in the 'Randomization' eCRF page)
 - Corticosteroids dose \leq 15 mg of prednisone-equivalent (reference level)
 - Corticosteroids dose $>$ 15 mg of prednisone-equivalent
- Treatment with antiviral therapy (AVT) including convalescent serum within 48 hours from randomization (as collected in the 'Randomization' eCRF page)
 - No (reference level)
 - Yes

Demographic characteristics:

- Age (derivation described at Section 11.1)
 - Age $<$ 60 (reference level)
 - Age \geq 60
- Gender
 - Male (reference level)
 - Female
- Ethnicity
 - Hispanic or Latino
 - Not Hispanic nor Latino (reference level)

Other characteristics:

- Country
 - United States of America (reference level)
 - Philippines
 - Brazil
- Site
- Smoking status at study entry (as collected in the ‘Substance Usage’ eCRF page)

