11.1 Demographics

Demographic characteristics and physical measurements will be summarized descriptively using the following information from the ‘Demography’ and ‘Screening Vital Signs’ eCRF pages.

The following demographic characteristics will be included:

- Sex: male, female
- Race: white, black or African American, Asian/ Pacific Islander, American Indian or Alaska Native, more than one race, other, unknown
- Ethnic origin: Hispanic or Latino/Not Hispanic or Latino
- Age (years)
- Age categories:
 - < 60 years,
 - ≥ 60 years
- Country: Brazil, Philippines, United States of America
- Site
- Height (cm) at Baseline

- Weight (kg) at Baseline
- BMI (kg/m²) at Baseline
 - < 30 kg/m²,
 - ≥ 30 kg/m²

Specifications for computation:

- Age [years]
 - (date of given informed consent - date of birth + 1) / 365.25
 - In case of missing day for at least one date, but month and year available for both dates: For the derivation of age, the day of informed consent and the day of birth will be set to 1 and the formula above will be used
 - In case of missing month for at least one date, but year available for both dates: For the derivation of age, the day and the month of informed consent and the day and month of birth will be set to 1 and the formula above will be used

The integer part of the calculated age will be used for reporting purposes.

- BMI [kg/m²] = $\frac{\text{weight [kg]}}{\text{height[cm]}^2} \times 10000$

All demographic data will be reported in listings.

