11.3 Other Baseline Characteristics

Tobacco consumption will be collected in the ‘Substance Usage’ eCRF page. The following information will be summarized together with demographic characteristics:

- Tobacco Status;

The following disease history characteristics will be summarized overall and by treatment group:

- Based on data from ‘Medical History’ eCRF page
 - Time since COVID-19 symptoms onset (days)
 - Time since diagnosis (days)

- Presence of the following co-morbidities:
 - Diabetes
 - Heart disease
 - Obstructive lung disease
 - Other lung disease
 - Chronic liver disease
 - HIV
 - Tuberculosis
 - Central nervous system disease
 - Hypertension
- Based on data from ‘COVID Symptom Assessment’ eCRF page
 - Presence of each of the following COVID-19 symptoms at study entry
 - Cough
 - Fever
 - Myalgia
 - Diarrhea
 - Dyspnea
 - Fatigue/malaise
 - Loss of appetite
 - Loss of smell
 - Loss of taste

‘Time since’ disease history characteristics, in days, will be calculated as follows:

- Time since symptoms onset (days) = (Date of first administration of study treatment - Date of symptoms onset)
- Time since diagnosis (days) = (Date of first administration of study treatment - Date of diagnosis)

The following listings will be created:

- Tobacco use
- Co-morbidities

- COVID symptoms.

Baseline characteristics with respect to vital signs, and hematology/biochemistry will be part of Section 15 (Safety Analysis).

12 Previous or Concomitant Medications/Procedures

The following analyses will be performed based on the ITT/SAF analysis set by study treatment group.

Concomitant treatments are medications, other than study treatment, which are taken by participants any time during the on-treatment period, see Section 9.7.

Previous medications are medications, other than study treatment, which started before first administration of study treatments.

A medication may be classified as both concomitant and previous. The respective flags will be derived based on start and end date.

Partially or completely missing medication start and stop dates will be handled as described in Section 9.8.

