Estimation of the effect of each treatment dose (and 95% two-sided CI) separately compared to placebo will be based on hazard ratio from stratified Cox-model of recovery hazard rate, with terms for treatment group (each active treatment separately against placebo), use of corticosteroids at a prednisone equivalent daily dosage of ≤ 15 mg or > 15 mg within 48 hours prior to randomization, and country. Ties will be handled using the discrete method.

Cumulative distribution function for time to recovery will be estimated via Kaplan-Meier (product limit) method by treatment group and presented together with associated statistics (median time to recovery, recovery rates at Day 7, Day 14, Day 21 and Day 28) including the corresponding two-sided 95% CI. The estimates of the standard error (SE) will be computed using Greenwood's formula.

A large, bold, red watermark consisting of the letters 'C', 'C', and 'I' is centered on a black rectangular background. The letters are stylized and slightly overlapping.

CCI

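### The visible primary Cox model adjusts only for corticosteroid use and country; age, which is already collected, is left out of the main estimate

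*SAP*

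**What the plan says.** SAP 14.1.1 tests each dose against placebo with a one-sided stratified log-rank test. It then estimates the hazard ratio, with a two-sided 95% confidence interval, from a stratified Cox model "with terms for treatment group (each active treatment separately against placebo), use of corticosteroids" in the 48 hours before randomisation, and country.

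SAP Section 7 explains the short list: "The inclusion of all stratification factors is identified as a potential source of problems in the implementation and interpretation of statistical models". It therefore says that "use of corticosteroids before randomization and country will only be included, as deemed the most relevant factors". Antiviral use and obstructive lung disease become subgroup factors.

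Age appears in several other places:
- Protocol 5.1 makes it an eligibility criterion: "Are ≥ 18 to ≤ 75 years of age, at the time of signing the informed consent".
- SAP 11.1 derives it from the consent and birth dates.
- SAP 8.2 lists it as a subgroup factor, split at 60 years.
- Protocol Appendix 5 explains that the upper limit was raised to 75 "to reflect a higher risk group for COVID-19 pneumonia".

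Age is not a stratification factor in either part of the study (Protocol Section 7). SAP Section 9 calls all tests exploratory. The text directly after the primary model in SAP 14.1 is redacted.

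**The concern.** With about 50 participants per arm and ages from 18 to 75, the arms can differ in age by chance, and neither the randomisation nor the visible main model deals with that. If age predicts recovery, an estimate that ignores it is less efficient, and its hazard ratio lies closer to 1 than the age-conditional one.

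The stated reason for a small model does not obviously reach age. Section 7 is about the number of stratification factors, and a continuous covariate adds no strata. Because the study is exploratory, the Cox hazard ratio and its interval are a main basis for judging whether to go on. A cheap gain in precision there is worth having.

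**Working it through.** **Plan's own figure.** None can be reproduced. The visible text gives no target hazard ratio, power, event count or age effect. The sample-size part of Protocol Section 10 is redacted.

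**Inputs from the documents.** Total 150 (15 + 135), randomised 1:1:1, so 150/3 = 50 per arm and 100 per comparison. Follow-up for the endpoint is to Day 28. Strata: 2 corticosteroid levels × 3 countries = 6.

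**Does the reason for a small model cover age?** Six strata give on average 100/6 ≈ 17 participants per stratum in one comparison. Adding antiviral use would give 12 strata and 100/12 ≈ 8. A linear age term leaves the strata at 6 and costs one degree of freedom.

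**Chance imbalance.** With 50 per arm, the difference in mean age has a standard error of √(1/50 + 1/50) = 0.20 SD, so its 95% range is ±1.96 × 0.20 = ±0.39 SD. If the log hazard ratio is −0.30 per SD (HR 0.74), this moves the unadjusted log hazard ratio by roughly ±0.39 × 0.30 = ±0.12, a factor of about 0.89 to 1.12.

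**Simulation.** The six-stratum Cox model for one dose against placebo was fitted with and without linear age, in 4,000 trials per cell at one-sided 0.025 (matching the 95% interval). All of these settings are assumptions:
- exponential recovery with a placebo median of 10 days
- 12% failures at average age, more at older ages, censored at Day 28
- recovery times without ties, although the plan scores status daily

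There were about 67 to 77 events per comparison.

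| Age HR per SD | True HR 1.5: power without → with age | Gain (points) | True HR 1.8: power without → with age | Gain (points) |
|---|---|---|---|---|
| 1.00 | 24.7% → 24.9% | +0.3 | 46.1% → 45.6% | −0.6 |
| 0.90 | 24.5% → 24.6% | +0.1 | 46.0% → 46.5% | +0.6 |
| 0.82 | 23.8% → 25.0% | +1.2 | 43.5% → 46.0% | +2.4 |
| 0.74 | 23.0% → 25.6% | +2.5 | 41.4% → 44.9% | +3.5 |
| 0.61 | 20.3% → 27.0% | +6.7 | 36.1% → 44.9% | +8.8 |
| 0.50 | 16.6% → 24.4% | +7.8 | 29.3% → 42.4% | +13.1 |

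Gains are taken before rounding. The Monte Carlo standard error of each power is at most √(0.46 × 0.54/4,000) ≈ 0.8 points, so differences below about 1 point should be read as zero.

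Under no treatment effect, the rejection rate was 2.0 to 2.6% without age and 2.1 to 3.0% with age, against a nominal 2.5%. The 3.0% arose at the most extreme age effect.

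**Why base power is low.** The Schoenfeld formula is Φ(√(d/4) × |ln HR| − 1.96). For HR 1.5 and d = 70 it gives Φ(4.18 × 0.405 − 1.96) = 40%. The simulated figure is lower mainly because failures stay at risk to Day 28, which pulls the average estimate from 1.5 to 1.38. Stratification costs a little more.

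**Movement of the hazard ratio.** At true HR 1.8, the average estimate goes from 1.54 to 1.58 when the age HR is 0.74 per SD, and from 1.50 to 1.59 at 0.61.

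**Cross-check.** A second simulation used 50 v 50, true HR 1.7, an age SD of 12 years and 2,500 trials per scenario:
- Age HR 0.8 per 10 years (0.8^1.2 ≈ 0.77 per SD): power rose from 62.5% to 65.4%.
- Age HR 0.7 per 10 years (0.7^1.2 ≈ 0.65 per SD): power rose from 57% to 65%.
- No age effect: the two powers were 66.2% and 65.8%.

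Base power differs between the two simulations because their settings differ. The gains agree.

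**The case against.** Much of the case on the other side stands.

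- **A reader might infer that the model ignores prognosis altogether.** It does not. It includes corticosteroid use and country, which Section 7 calls the most relevant factors.
- **A reader might infer that the primary test loses power.** The planned test is the stratified log-rank test, and a covariate in the Cox model leaves it unchanged. The gains above belong to the Cox estimate, its interval and its Wald test.
- **A reader might infer that the documents show age to be a strong predictor of recovery.** They do not. The higher-risk remark is a rationale for widening eligibility and says nothing about speed of recovery among people who already have pneumonia. The subgroup list also holds sex, ethnicity, site and smoking, so being listed there does not establish prognostic strength.
- **A reader might infer that the unadjusted hazard ratio is biased.** At least part of the shift is a change of target. The hazard ratio is not collapsible, so the age-conditional ratio is a different quantity from the less conditional one now planned.
- **The study is exploratory and the SAP chose a small model for a stated reason.** No passage is contradicted. That reason is about stratification factors, however, and no visible text explains why one continuous term would be a problem.
- **The redaction limits the point.** The SAP's modification history says a sensitivity analysis was kept for the primary endpoint, but it cannot be seen. An age-adjusted supportive analysis cannot be ruled out. The main model itself is visible and has no age term.

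**Conclusion.** The point holds as a worthwhile low-cost improvement. The visible main estimate adjusts only for corticosteroid use and country and leaves age out.

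The size depends wholly on an age effect that the documents do not give. Under the simulated settings, the gain in Wald-test power is about zero if age is weakly prognostic, about 3 points if moderate (HR about 0.75 per SD), and about 7 to 9 points if strong (HR about 0.6 per SD). The balance favours inclusion: if age is irrelevant the change is under 1 point, and the false-positive rate stays near nominal.

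The documents do not support calling the present model invalid, or saying that a known amount of power is being lost.

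**What to change.** Before unblinding, amend SAP 14.1.1 so that the stratified Cox model for time to recovery has age (continuous, in years) as one added pre-specified covariate. Make the same change in SAP 14.2.3 for time to SpO2 improvement. SAP 14.2.9 refers to that section for time to hospital discharge, so the change carries over, but it should be stated there.

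Say that the reported hazard ratio is conditional on age, and report the current model as supportive. Leave the stratified log-rank test as planned, and note that it is not age-adjusted. If the redacted text already holds an age-adjusted analysis as supportive, the change is only which of the two models is named as main.

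Time since symptom onset, summarised at baseline in SAP 11.3, could be added as well. That is optional and its effect was not evaluated.

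The cost is a few sentences and one model term on data already collected. The one real trade-off is the move to an age-conditional hazard ratio.

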 - Smoker (former, or regular tobacco use)
 - Non-Smoker (never used tobacco, reference level)

Subgroup analyses will be performed on primary and selected secondary efficacy endpoint as defined below. CCI

For the definition of subgroup level, data as documented in the eCRF will be taken. The category “missing” will not be included in any subgroup analysis.

For subgroups with two categories only, in case of less than 9 participants within each category the subgroup will not be considered for the analysis.

CCI

9 General Specifications for Data Analyses

This section describes any general specifications not included in subsequent sections.

Part A objectives will be separately described only in case of early termination of the study for safety reasons, otherwise all data from all study participants from Part A and Part B will be combined.

Study treatment groups are defined and labeled as Placebo, M5049 50 mg BID, and M5049 100 mg BID. Unless otherwise indicated, all tables will be presented by study treatment groups. For demographics, baseline and safety data a total column is also presented.

The “start date” for this study is the first dose date (Day 1).

Unless otherwise specified, comparisons will be presented for each dose of M5049 versus placebo.

In this study there will be no hypothesis testing; therefore, all statistical tests mentioned in this IAP are to be regarded as exploratory. Exploratory statistical tests comparing study treatment groups will be performed two-sided and confidence intervals (CI) will be two-sided with a confidence probability of 95%, unless otherwise specified in this IAP.

All analyses will be performed using SAS® Software Version 9.2 or higher, with the exception of M5049 PK parameters which will be derived using noncompartmental methods with the validated computer program PPD [REDACTED] or higher PPD [REDACTED].

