9.5 Definition of Duration and ‘time since’ Variables

Durations in days will be calculated by the difference of start and stop date/time (e.g. survival time (days) = date/time of death – date/time of first dose) if not otherwise specified.

The time since an event (e.g. time since diagnosis) will be calculated as reference date/time minus date/time of event, when available.

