14.1 Primary Endpoint: Time to Recovery

14.1.1 Primary Objective: Derivation and Analysis of the Primary Endpoint Time to Recovery

The primary efficacy variable is the time to recovery, defined as the time from first dose (Day 1) through Day 28 to first occurrence of WHO 9-point ordinal scale 3 or less, in days:

- Time to recovery (days) = (Date/time of first ordinal scale for clinical severity <= 3 – Date/time of first dose)

The rules for the different types of censoring/event below will be followed:

| # | Description | Date of Response or Censoring | Outcome |
|---|---|---|----------|
| 1 | Death from Day 1 up to D60/Study completion | D28 | Censored |
| 2 | Failure at any point and time during the study from D1 up to D28, defined as: * ICU admission leading to treatment discontinuation * use of mechanical ventilation * relapse | D28 | Censored |
| 3 | Participant not confirmed to be eligible based on inclusion criterion 6 (PDEV05 code) | Date of first dose of study drug | Censored |
| 4 | No post-baseline clinical status data | Date of first dose of study drug | Censored |
| 5 | Clinical status ≤ 3 before Day 28 | Date of clinical status ≤ 3 | Event |
| 6 | Clinical status > 3 through Day 28 without death or failure | D28 | Censored |
| 7 | Early discontinuation before or on Day 28 without improvement, failure or death | Date/time of last available result of clinical status from Day 1 through Day 28 | Censored |

Number and percentage of participants with and without recovery will be presented.

The hypotheses that will be tested for each dose level using a one-sided stratified log-rank test of distribution of time to recovery with use of corticosteroids at a prednisone equivalent daily dosage of ≤ 15 mg or > 15 mg within 48 hours prior to randomization, and country as stratification factors, are:

- $H_{0i}: HR_i \leq 1$

- $H_i: HR_i > 1$

where

- HR_i denotes the Hazard Ratio of M5049 dose i versus placebo
- i denotes M5049 50 mg BID or M5049 100 mg BID
- $HR_i > 1$ denotes an improvement compared to placebo.

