14.2.2 Clinical Status

Clinical status will be based on data collected on the ‘Ordinal Scale for Clinical Status’ eCRF page and is assessed with the following ordinal scale:

0. Uninfected: no clinical or virological evidence of infection.
1. Ambulatory: no limitation of activities.
2. Ambulatory: limitation of activities.
3. Hospitalized, mild disease: hospitalized, no oxygen therapy.
4. Hospitalized, mild disease: oxygen by mask or nasal prongs.
5. Hospitalized, severe disease: noninvasive ventilation or high-flow oxygen.
6. Hospitalized, severe disease: intubation and mechanical ventilation.
7. Hospitalized, severe disease: ventilation + additional organ support – e.g., pressors, RRT, ECMO
8. Death.

In case of death, the participant will be counted with the clinical status =8 (death) for any scheduled timepoint after death date. There will be no imputation of missing data.

Clinical status is expected every day during hospitalization and then at every scheduled visit after discharge. Day 1 assessment will serve as baseline measurement. If missing, the last non-missing measurement prior to randomization will be used.

The number and percentage of participants in each clinical status category as well as summary statistics for absolute and change from baseline status will be presented by treatment group, in a tabular and graphical form, using a stacked bar chart.

A cumulative logit model will be used to compare the clinical status results of each M5049 group versus placebo at the following analysis visits: Day 7, Day 14, Day 21, Day 28, Day 44 and Day 60 according to the ordinal scale described above. Under the assumption of proportional odds, the odds ratio (OR) and its 95% Wald CI will be estimated for each M5049 group versus placebo. A score test for the proportional odds assumptions will be reported.

Should the model fail, due to an insufficient number of observations per category of the dependent variable, then relevant categories may be collapsed.

In addition, the following dichotomized versions of the clinical status will be derived, only if at least 6 participants in each level are present:

- Death (clinical status = 8) versus any other category (clinical status \neq 8)
- Worsening (clinical status \geq 5) versus stable/improvement (clinical status $<$ 5)
- In-hospital (clinical status \geq 3) versus hospital discharged (clinical status $<$ 3).

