14.2.9 Total Days in the Hospital and Time to Hospital Discharge

Total days in the hospital will be based on data collected on the ‘Hospitalization’ eCRF page.

Total days in the hospital are defined as the sum, for all hospitalization events, of the time from first dose to the date of hospital discharge, in days:

- Total days in the hospital (days) =
 First hospitalization: *Date of hospital discharge – Day 1 + 1*
 +
 Subsequent hospitalization: *Date of discharge – date of admission + 1*

In other words, in case of hospital admission prior to and discharge after first dose, date of first dose will be used in place of date of hospital admission for calculation of total days in the hospital. In case of multiple hospitalizations, the total number of days of each event will be added up.

The following information will be presented:

- Number and percentage of participants with more than one hospital admission (only non-consecutive hospitalization will be included in the count)
- Number and percentage of participants in the following discharge categories: death in hospital, discontinuation in hospital, discharged from hospital.
- Summary statistics of duration of hospital stay.

In addition, time to hospital discharge will be based on data collected on the ‘Hospitalization’ eCRF page from Day 1 through Day 28.

The time to hospital discharge, defined as the time from first dose (Day 1) to the date of first hospitalization discharge, in days:

- Time to hospital discharge (days) = (Date of first hospitalization discharge – Date of first dose)

The rules for the different types of censoring/event below will be followed:

| # | Description | Date of Event or Censoring | Outcome |
|---|-------------|----------------------------|---------|
|---|-------------|----------------------------|---------|

| | | | |
|---|---|--|----------|
| 1 | Death from Day 1 up to D60/Study completion | D28 | Censored |
| 2 | Failure at any point and time during the study from D1 up to D28, defined as: * ICU admission leading to treatment discontinuation * use of mechanical ventilation * relapse | D28 | Censored |
| 3 | Hospital discharge before Day 28 | Date of hospital discharge | Event |
| 4 | No hospital discharge before Day 28/discontinuation without death or failure | Earliest between D28 and date of discontinuation | Censored |

Analyses will be performed as specified in Section 14.2.3.

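### The Cox models are said to give hazard ratios, but the discrete tie method gives an odds ratio when times are tied: certain for time to hospital discharge, conditional for recovery, and small in size

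*SAP*

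**What the plan says.** For the primary endpoint, SAP 14.1.1 estimates each dose effect by a "hazard ratio from stratified Cox-model of recovery hazard rate, with terms for treatment group (each active treatment separately against placebo"), with corticosteroid use and country also in the model, and gives a two-sided 95% interval. It then says: "Ties will be handled using the discrete method". The same tie rule stands in 14.2.3 (time to SpO2 improvement) and 14.2.5 (time to ICU admission). Sections 14.2.6 and 14.2.7 (ventilation) take their analysis from 14.2.5, and 14.2.9 (hospital discharge) takes it from 14.2.3. On software, SAP Section 9 says: "All analyses will be performed using SAS® Software Version 9.2 or higher".

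The time unit differs between places:

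- The 14.1.1 formula starts from "Date/time of first ordinal scale for clinical severity <= 3" and subtracts the date/time of first dose.
- The event row of the 14.1.1 censoring table gives "Date of clinical status ≤ 3", while the early-discontinuation row of the same table uses date/time.
- The general rule in 9.5 is: "Durations in days will be calculated by the difference of start and stop date/time".
- Time to hospital discharge in 14.2.9 runs from the date of first dose to the "date of first hospitalization discharge", with no clock time at either end.

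Nothing in the SAP says that the tie option changes the model or that the estimate may be an odds ratio.

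**The concern.** The discrete option is not a third approximation to the Cox likelihood alongside Breslow and Efron. It replaces the proportional-hazards model by a logistic model for the event at each distinct time. Its parameter is a log odds ratio, while the parameter defined in the SAP's hypotheses is a hazard ratio. The two agree when no event times coincide and separate as ties accumulate, always with the odds ratio further from 1.

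Section 9 calls all tests exploratory, so the estimates and intervals are the main product of this study. They should be the quantity their label names, and a shift away from no effect is an unwelcome direction for a labelling error.

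**Working it through.** **Inputs from the documents.** 150 participants randomised 1:1:1, so about 50 per arm (protocol 4.1). Follow-up for the endpoint is to Day 28. The protocol's summary of changes quotes median recovery times of 7 to 9, 10 and 15 days, and a median hospital stay of 16 days. The readable text gives no assumed treatment effect and no figure for this estimate, so there is nothing to reproduce first.

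**Assumptions.** *Discrete method* means the SAS Cox-procedure option of that name. True hazard ratios of 1.25, 1.5 and 2.0 are tried, with exponential event times.

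**Step 1: what the likelihood estimates.** At a time with d events, the discrete likelihood conditions on d and compares the observed set of events with every possible set of size d from those at risk. That is conditional logistic regression. With d = 1 it reduces to the ordinary Cox term, so it departs from Cox only at tied times.

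**Step 2: where ties arise.**

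- Discharge: whole days at both ends, so tied by construction.
- Recovery by date/time: first-dose times differ between participants, so exact ties would be rare even with once-daily scoring.
- Recovery by date: heavily tied. In its favour, protocol 9.1.3.1 records the score against the study day, SAP 14.2.2 says "Clinical status is expected every day during hospitalization and then at every scheduled visit after discharge", and SAP 9.8 has rules for missing clock times of adverse events, doses and ICU stays but none for the ordinal scale.

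**Step 3: size with whole-day times.** If hazards are proportional with placebo daily hazard h = ln 2 / median, the placebo daily probability is p0 = 1 − exp(−h), and the daily odds ratio is

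OR = [exp(HR × h) − 1] / [exp(h) − 1].

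| Median (days) | p0 | HR 1.5 reads | HR 2.0 reads |
|---|---|---|---|
| 7 | 0.094 | 1.538 | 2.104 |
| 10 | 0.067 | 1.527 | 2.072 |
| 15 | 0.045 | 1.518 | 2.047 |
| 16 (hospital stay) | 0.042 | 1.516 | 2.044 |

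At round values, p0 = 0.05 gives 1.520 and 2.053, and p0 = 0.10 gives 1.541 and 2.111. For a protective effect, HR 0.67 reads 0.659 at a 7-day median.

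**Step 4: simulation.** 300 runs per scenario, 50 versus 50, 10% in both arms never recovering, follow-up to Day 28, six strata (two corticosteroid levels by three countries) or none. Each likelihood was fitted to the same data. Whole-day times with six strata:

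| True HR | Median (days) | Events tied | Efron HR | Discrete OR | Ratio |
|---|---|---|---|---|---|
| 1.25 | 7 | 56% | 1.178 | 1.185 | 1.006 |
| 1.25 | 10 | 49% | 1.192 | 1.199 | 1.006 |
| 1.5 | 7 | 58% | 1.375 | 1.395 | 1.015 |
| 1.5 | 10 | 51% | 1.353 | 1.368 | 1.011 |
| 2.0 | 7 | 61% | 1.628 | 1.669 | 1.025 |
| 2.0 | 10 | 54% | 1.695 | 1.733 | 1.022 |

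All estimates fall below the true value because of the non-recovering fraction; the comparison of interest is between methods. The 95th percentile of the ratio was 1.03 to 1.06, and the largest in any run about 1.10. Without strata, 93% of events were tied and the average ratio was 1.006 to 1.021. With continuous times, Breslow, Efron and discrete were identical in every scenario (for example 1.360 for all three at HR 1.5, 7 days, six strata).

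**Step 5: against the sampling error.** With roughly 80 recoveries per comparison (assumed), the standard error of the log hazard ratio is about 2/√80 = 0.224. Each 95% limit then lies a factor exp(1.96 × 0.224) = 1.55 from the estimate, so a shift of 1% to 3% is small beside it.

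**The case against.** A reader might infer that the primary effect estimate is mislabelled and exaggerated outright. The documents do not support that. The primary formula and Section 9.5 use date/time, and the SAP's modification history says first-dose date/time is used for all such calculations. If clock times are recorded, ties are rare and the discrete estimate equals the Cox hazard ratio. Only the event row and the day-level recording point the other way, so for recovery this is an unresolved inconsistency.

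A reader might also infer a larger distortion. A daily probability of 0.20 would turn 1.5 into 1.59 and 2.0 into 2.25, but it implies a median of ln 0.5 / ln 0.8 = 3.1 days, against the 7 to 15 days the protocol quotes.

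Nor can it be inferred that inference is spoiled. The stratified log-rank test does not use the tie option and is in fact the score test of the discrete model. The Kaplan-Meier medians and recovery rates, which are what protocol 10.4.2 itself specifies for the primary endpoint, do not use it either. The protocol's rationale calls time to recovery a widely used endpoint; it promises nothing about comparing hazard ratios across trials.

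These points stand, and they limit the finding to labelling and a small numerical shift. The remaining argument, that a discrete-time model is legitimate for outcomes recorded by day, is correct but does not rescue the text: such a model is acceptable only if its estimate is not called a hazard ratio.

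**Conclusion.** The point holds in limited form. For time to hospital discharge, the estimate called a hazard ratio will be a discrete-time odds ratio, with no assumption needed about clock times. For recovery, the same is true only if both ends are timed in whole days, which 14.1.1 does not settle; 14.2.3 mixes date/time and date in the same way. For ICU admission and ventilation, low daily event probabilities would make any shift smaller still. The shift is always away from 1, and none of it changes a test or a Kaplan-Meier estimate. The conclusion rests on the SAS reading of the tie option; the sizes rest on the assumed effects, exponential times and, in the simulation, the non-recovering fraction and the mix of strata.

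**What to change.** In SAP 14.1.1, 14.2.3 and 14.2.5, name the Efron method (or the exact method) for ties in place of the discrete one. Sections 14.2.6, 14.2.7 and 14.2.9 inherit the change. In 14.1.1, use one time unit for recovery, date or date/time, in both the formula and the censoring table. If the discrete method is preferred because outcomes are recorded by day, keep it and label the estimates as discrete-time odds ratios wherever times are in whole days.

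The cost is one word in three places and one clarification. Where there are no ties the results do not change; where there are, the estimate targets the hazard ratio that the SAP defines.
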